6 STUDY OBJECTIVES AND ENDPOINTS

6.1 Objectives

The primary objective of the study is to investigate the effect of GRF6021 on intracellular signaling cascades in blood leukocytes as determined by CyTOF. Secondary objectives include evaluation of the effect of GRF6021 on clinical recovery parameters in patients undergoing primary hip or knee arthroplasty, safety and tolerability of GRF6021, and the effects of GRF6021 on plasma proteomics.

6.2 Endpoints

- Primary Endpoint (analyses detailed in this SSAP):
 - Effect of GRF6021 on intracellular signaling cascades in blood leukocytes as determined by CyTOF.
- Secondary Endpoints (analyses detailed in this SSAP):
 - Change in functional status using the ActiGraph wearable device providing measurements for physical activity/function and sleep (starting at least 3 days prior to surgery and continuing until the end of the study).
 - The effects of GRF6021 on plasma proteomics.
- Secondary Endpoints (analyses detailed in the SAP [08OCT2020]):
 - Change from baseline in 3-Minute Diagnostic Interview for Confusion Assessment Method (3D-CAM).
 - Time to 50% recovery of baseline value on the Surgery Recovery Scale (SRS).
 - End of study (EOS) treatment comparison of the Western Ontario and McMaster Universities Osteoarthritis Index (WOMAC).
 - Time to a score of < 12/40 on a subset of questions from the WOMAC, Pain Subscale.
 - Time to a score of < 18/60 on a subset of questions from the WOMAC, Physical Function Subscale.
 - Change from baseline in the Short Form-36 (SF-36).
 - Change from baseline in the Beck Depression Inventory-II (BDI-II).
 - Opioid analgesic consumption during hospital stay and after discharge to EOS.
 - Time to discharge.
 - Perioperative outcomes (e.g., surgery duration, anesthesia duration, post-anesthesia care unit (PACU) stay duration, American Society of Anesthesiologists (ASA) status, estimated blood loss (EBL), type and amount of intraoperative fluids administered, type and amount of intraoperative blood products, dose and type of anesthesia (general, regional), and intraoperative opioid dose).
 - Change from baseline in clinical laboratory parameters.
 - Change from baseline in vital sign measurements.
 - Change from baseline in electrocardiogram (ECG).

7 STUDY OVERVIEW

7.1 Study Design and Treatment Groups

This is a randomized, placebo-controlled, double-blind pilot study to investigate the effects of GRF6021, a 5% human plasma protein fraction administered by intravenous (IV) infusion, on intracellular signaling cascades in blood leukocytes in subjects undergoing primary hip or knee arthroplasty.

The study will enroll approximately 45 subjects with the aim of having 40 evaluable subjects randomized in a 1:1 ratio to active treatment or placebo.

Each subject will receive 4 infusions of 250 mL GRF6021 or 4 infusions of 250 mL placebo (normal saline):

- 1) 1 infusion on the day before surgery
- 2) 1 infusion on the day of surgery within 4 hours before surgery start (first incision)
- 3) 1 infusion on the day of surgery upon arrival in the postoperative care unit (within 5 hours after the first incision)
- 4) 1 infusion on the day after surgery

Each infusion will be administered over approximately 30 minutes, and the infusion procedure of active and placebo agents will be identical to maintain the blind.

In this study, CyTOF, a multiplexed, high-content immune profiling technology, will be used to provide high-resolution surveillance of circulating immune cells and the response to GRF6021 infusions on surgical recovery. The Somalogic SomaScan platform (Somalogic, Boulder, Colorado, US), which is an affinity-based targeted proteomics approach, will be used to measure plasma protein levels. Blood samples for both CyTOF and proteomics will be collected at baseline (Visit 3) and 3 perioperative time points (Visits 4a, 4b, and 5).

At screening, subjects will be provided with an ActiGraph wearable device ([ActiGraph 2021](#)). Approximately -7 to -3 days prior to surgery, subjects will be instructed to wear the device which will then begin monitoring specific measurements of physical activity, mobility, and sleep. Data collection is ongoing, and subjects will wear the device until admission, except during Visits 4a and 4b when it is removed for surgery.

Additional functional and quality of life assessments will be measured at baseline and at various times after the surgery (detailed information regarding assessments can be found in the study protocol [V3.0, 14NOV2019]). Analysis of these secondary endpoints are detailed in the SAP (08OCT2020).

7.2 Statistical Hypothesis

The hypothesis is that active treatment with GRF6021 will modulate the immune response and/or proteomics profiles to surgery differently as compared to placebo, and will change the postoperative functional status measured by the ActiGraph wearable device. Machine learning approaches will be utilized to detect immune features (functional cellular attributes as well as

cell abundance) and/proteomics features, as well as ActiGraph measurements that separate the active and placebo groups.

It is also hypothesized that there are immunomodulatory changes significantly associated with postoperative recovery in this study ([Gaudillière 2014](#)).

7.3 Sample Size Justification

As detailed in the protocol, the goal is to enroll a total of approximately 45 subjects with the aim of having 40 evaluable subjects randomized in a 1:1 ratio to active treatment or placebo groups. Due to the coronavirus disease 2019 (COVID-19) pandemic, enrollment ended with 37 evaluable subjects. Evaluable subjects are those who received all 4 doses and had all blood draws for assessment of the primary endpoint. Previous work demonstrated that a sample size of approximately 40 subjects enabled the detection of clinically-relevant immunomodulatory changes, such as changes in signaling downstream of immune receptors, including interleukin-1 and toll-like receptor 4 ([Aghaeepour 2017](#), [Davis 2020](#)).

7.4 Randomization and Blinding

The study will be randomized in a 1:1 ratio (active: placebo), stratified by sex and surgical joint (hip, knee) to assure a balanced distribution of evaluable male and female subjects in both treatment groups.

7.5 Interim Analysis

No interim analyses are planned.

7.6 Study Assessments and Time Points

The study design consists of 15 protocol-specified visits which will be assessed as nominal visits from an analysis perspective ([Table 1](#), [Figure 1](#)):

[figure not shown]
- 1) Visit 1 Screening (Day -42 to -3).
- 2) Visit 2 Baseline (Days -7 to -3): Subjects will be contacted by phone to obtain the remote Baseline Visit assessments. Subjects will be randomized after eligibility has been confirmed.
- 3) Visits 3 through 5, Treatment (Days 1-3): on-site Baseline assessments will be gathered prior to the first infusion on Day 1. After the first infusion on Day 1, the subject will be discharged from the facility and come back the following morning (Day 2) for the inpatient period. The inpatient treatment period is 2 days during which each subject will receive 3 additional doses of 250 mL of their assigned treatment allocation.
- 4) Visits 6 through 14 (Day 4 through Day 37±2): these are the follow-up visits, which will be conducted remotely by phone and/or electronically.
- 5) Visit 15, EOS (Day 44±2): the EOS Visit will be conducted remotely by phone and/or electronically.
- 6) Early termination: If a subject has received at least one infusion but is terminated or terminates from the study early, the site should try to perform all assessments scheduled at

the EOS Visit (Visit 15) and complete the exit lab panel if the subject is still at the site and available and willing.

Table 1. AKST6021-211 Study Visits

Visit	Screening (On-site)	Baseline Visit (Remote)	Baseline Visit (On-site)/ Treatment (On-site)					Follow-up/End of Study (EOS) (Remote)									
			3	4 ^a	4 ^b	5	6	7	8	9	10	11	12	13	14	15	
Visit	1	2	3	4 ^a	4 ^b	5	6	7	8	9	10	11	12	13	14	15	
Infusion Number			1	2	3	4											
Postoperative day			-1	0	0	1	2	4	7	10	14	17	21	28	35	42	
Day	Day -42 to -3	Day -7 to -3	1	2	2	3	4	6±1	9±1	12±1	16±1	19±1	23±2	30±2	37±2	44±2	
Week	-6 to -1	-1		1			1	1	1	2	2	3	3	4	5	6 EOS	

Figure 1. Study Schematic

8 STATISTICAL METHODOLOGY

8.1 General Considerations

This section of the SSAP presents the analytical approaches that are anticipated for the high-dimensional data from AKST6021-211. Analysis of data from the clinical secondary endpoints from AKST6021-211 are detailed in the SAP (08OCT2020). These analytical approaches to the high-dimensional data may at times require modifications due to unanticipated features.

Deviations from analyses summarized in this document will be noted in the Clinical Study Report (CSR).

All analysis dataset preparations and statistical analyses will be performed using R version 4.0.2 or higher.

The high-dimensional data results from AKST6021-211 will be analyzed using the immunological elastic net (iEN) algorithm for the primary endpoint and standard elastic net (EN) modeling for the ActiGraph and proteomics data. Models utilizing iEN or EN utilize a penalized regression method particularly adapted to the analysis of highly-correlated data, as it eliminates redundant parameters while retaining interrelated parameters (Zhou 2005, Culos 2020). All parameters will be set to default except for $\alpha = 0.5$ (to limit the number of selected features, but account for the most important components of each intracorrelated module) and standardized as equal to FALSE to enable the specific modifications described in [Section 8.4 Efficacy Analyses](#). A two-layer leave-one-out cross-validation strategy will be employed where the final model will have optimized the segregation of active versus placebo treatment groups. The internal layer will optimize the free parameters of the model, and the external layer will evaluate model performance. Data presentations will include a flow diagram of the progress of the 2 groups (GRF6021 and placebo) through enrollment, intervention allocation, follow-up, and data analysis. Additional multi-part visualizations (figures) for the primary endpoint (CyTOF) and select secondary endpoints (ActiGraph, proteomics) will be developed (see [Appendix 1](#)).

Unless otherwise specified, an alpha of 0.05 will be used for significance testing. For multiple comparisons due to the high dimensionality, the false discovery rate using the Benjamini-Hochberg method will be controlled and the corrected p-values will be reported as q-values.

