20. Myeloid dendritic cells (mDCs), and	
21. Plasmacytoid dendritic cells (pDCs)	

Measurement of CyTOF will be performed by Dr. [REDACTED] and Dr. [REDACTED] ([REDACTED]). Two (2) CyTOF datasets will be generated and analyzed separately:

- *CyTOF Dataset 1* (Effect on endogenous immune responses to surgery): Changes in cell frequency and endogenous intracellular signaling activities from Visit 3 to Visits 4b and 5.
- *CyTOF Dataset 2* (effect on immune response to *ex vivo* stimulation): Changes in cell frequency and evoked intracellular signaling responses to *ex vivo* stimulations from Visit 3 to Visit 4a.

Cell frequencies will be expressed as percentages of gated singlets in the case of granulocytes, and as percentages of mononuclear cells in the case of all other cell types. For each cell type,

frequency features will be calculated as the difference in cell frequency between Visit 3 and Visit 4b or Visit 5 (Dataset 1) or Visit 3 and Visit 4a (Dataset 2).

For each cell type, basal signaling activities will be expressed as the median signal intensity (arcsinh transformed value) of each signaling protein.

Endogenous signaling changes in response to surgery will be expressed as the difference in median signal intensity (hyperbolic arcsine [arcsinh] ratio) between post-operative time points (Visit 4b, Visit 5) and the day of surgery, preoperative time point (Visit 4a).

Evoked signaling responses to stimulations will be expressed as the difference in median signal intensity (arcsinh ratio) between the stimulated and unstimulated condition. Changes in evoked signaling responses will be expressed as differences in evoked signaling responses between the Visit 3 (baseline) time point and the Visit 4a time point.

The high-dimensional data results will be further analyzed and presented using the iEN algorithm which is a penalized regression method particularly adapted to the analysis of highly-correlated data, as it eliminates redundant parameters while retaining interrelated parameters (for further details see [Section 8.1 General Considerations](#)). Data presentations will include multi-part visualizations (figures) (see [Appendix 1](#)).

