8.4.2 Select Secondary Endpoints (High-Dimensional Data)

8.4.2.1 Change in Functional Status using the ActiGraph Wearable Device

The ActiGraph wearable device is used to monitor subjects' physical activity, mobility and sleep ([ActiGraph 2021](#)). Functional status including heart rate and sleep time will be collected during the whole study period except perioperative times. Changes in functional statuses comparing to the baseline will be calculated. The complete list of 62 ActiGraph measurements can be found in the ActiLife 6 User's Manual ([ActiGraph 2012](#)).

The ActiGraph high-dimensional data will be analyzed and presented using the EN algorithm which is a penalized regression method particularly adapted to the analysis of highly-correlated data, as it eliminates redundant parameters while retaining interrelated parameters (for further details see [Section 8.1 General Considerations](#)). Data presentations will include multi-part visualizations (figures) (see [Appendix 1](#)).

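### SAP 8.1 turns feature standardization off for every elastic-net model and cites modifications in 8.4 that are not there, so measurement scale partly decides which features are selected

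*SAP*

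**What the plan says.** SAP 8.1 assigns the immunological elastic net (iEN) to the CyTOF primary endpoint and "standard elastic net (EN) modeling for the ActiGraph and proteomics data". It then treats the two methods together and lists only two departures from default settings. One is a mixing alpha of 0.5, chosen "to limit the number of selected features, but account for the most important components of each intracorrelated module". The other is that features are "standardized as equal to FALSE to enable the specific modifications described in" Section 8.4. Neither is limited to one model.

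Section 8.4 describes how features are built:

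- **CyTOF (8.4.1).** "Cell frequencies will be expressed as percentages of gated singlets in the case of granulocytes", and relative to mononuclear cells for other cell types. Signaling features are on an arcsinh scale: "Endogenous signaling changes in response to surgery will be expressed as the difference in median signal intensity".
- **ActiGraph (8.4.2.1).** "Functional status including heart rate and sleep time will be collected", with changes from baseline computed. No units are given. "The complete list of 62 ActiGraph measurements can be found in" an external user's manual.
- **Proteomics (8.4.2.2).** About 7,000 proteins in relative fluorescence units (RFU), with no log transform or rescaling stated. CyTOF and proteomics data may also be combined in one model, and Appendix 1 has figure shells for it.

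For model details, each part of 8.4 sends the reader back to 8.1. In 8.4.1 the method "eliminates redundant parameters while retaining interrelated parameters (for further details see" Section 8.1.

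**The concern.** An elastic net penalizes the size of coefficients, and a coefficient's size depends on the unit of its feature. Default software therefore standardizes features first. The SAP turns this off for a reason it does not supply: 8.1 points to 8.4, and 8.4 points back to 8.1. No scaling, prior weight or penalty factor appears in either place.

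At stake is the study's main product. Protocol 10.4.2 makes a list of features the output of the primary analysis, and SAP Figure 14.2.9 reports the features the net selects. If scale enters the selection, the list partly reflects units and variance instead of association with treatment. Since this is an exploratory pilot, the harm is a misleading list for later work to build on, not a false efficacy claim.

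**Working it through.** **1. What follows from the penalty, without assumptions about data.** Take a centred feature x_j alone, treatment indicator y, sample size n and mixing alpha a. It enters the model at

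λ_j = |x_j′(y − ȳ)| / (n·a) = SD(x_j) · |r_j| · SD(y) / a,

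where r_j is its correlation with treatment. SD(y) and a are common to all features, so first entry is ranked by SD × |r|. A feature with three times the SD needs one third of the correlation to enter at the same point. Hours to minutes multiplies λ_j by 60 with the data unchanged. After standardization SD = 1 for all features and the ranking is by |r| alone.

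The coefficient update divides by v_j + λ(1 − a), where v_j is the feature variance. If all features are multiplied by c, λ scales with c and v_j with c², so the ridge share λ(1 − a)/v_j scales with 1/c. The balance that alpha = 0.5 is meant to fix therefore depends on absolute units.

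**2. Inputs for the illustrations.** From the documents: 37 evaluable subjects (SAP 7.3), 1:1 allocation, alpha 0.5, 62 ActiGraph measures, about 7,000 proteins, 21 cell types and 11 signaling markers (SAP Table 2). CyTOF Dataset 1 has two postoperative visits, giving 21 × 2 = 42 frequency and 21 × 11 × 2 = 462 signaling features, 504 in all.

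Assumed: a 19/18 split, all SDs, independent features, the number of true features, and a standardized difference d = 1.2 unless stated. The model is a Gaussian elastic net on treatment group, with λ at minimum leave-one-out error (10-fold cross-validation for the 7,000- and 7,504-feature runs). FALSE and training-fold z-scoring were run on the same simulated data, with 250 trials per ActiGraph setting, 150 to 200 for CyTOF, and 60 for proteomics and combined. AUC is from an external test set of 400.

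**3. ActiGraph-like model (62 measures, 5 true).** True features found, of list length:

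| SD spread | FALSE | Standardized | AUC, FALSE vs standardized |
|---|---|---|---|
| Equal | 4.5 of 14.3 | 4.7 of 17.1 | 0.91 vs 0.91 |
| 10-fold | 3.3 of 12.4 | 4.6 of 15.9 | 0.85 vs 0.91 |
| 100-fold | 2.2 of 10.5 | 4.6 of 15.5 | 0.79 vs 0.91 |

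List length does not explain this. Among the first 10 or so features to enter, FALSE finds 3.1 (10-fold) and 2.2 (100-fold), against 4.6. With d = 0.8 and a 10-fold spread the figures are 2.3 of 10.0 against 3.5 of 14.3.

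One unit on its own: sleep time with SD 1 h (60 min), other SDs 2.4 to 24.5.

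| Sleep time selected | Hours | Minutes | Standardized |
|---|---|---|---|
| It truly differs | 0% | 99.6% | 92% |
| It does not differ | 0% | 74% | 23% |

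**4. Combined model (504 CyTOF + 7,000 proteins, 10 true in each), CyTOF/protein true features.** Equal SDs: FALSE 5.7/5.9 of 34.6, standardized 5.6/5.9 of 40.6. With protein SDs three times larger, FALSE gives 0.0/6.1 of 25.3. From 3-fold to 100-fold, no CyTOF feature of any kind is selected.

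**5. CyTOF Dataset 1 (5 true in each block), fitted as a plain elastic net.** Signaling SD 0.2; frequency SD = ratio × 0.2.

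| SD ratio | Signaling/frequency true | List length |
|---|---|---|
| 0.1 | 4.7/0.0 | 43.9 |
| 1 | 4.5/4.5 | 45.9 |
| 3 | 1.6/4.7 | 23.2 |
| 10 | 0.0/4.6 | 12.5 |
| Standardized | 3.9/3.9 | 28.1 |

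The share of true features at ratios 3 and 10 is (1.6 + 4.7)/23.2 = 27% and 4.6/12.5 = 37%, against 7.8/28.1 = 28% standardized. Purity is not lost; what changes is which block disappears. The high count at ratio 1 comes from the longer list that SD 0.2 produces. With all SDs 1.0 the result is 3.9/3.8 of 25.1 against 4.0/3.9 of 26.4; with all SDs 0.05 the list grows to 112.5 against 28.8.

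No clean block difference is needed. With SDs spread 10-fold within each block and a block ratio of 1, FALSE gives 2.2/2.0 of 26.3 against 4.1/3.9 of 27.5 (AUC 0.83 vs 0.95). With d = 0.8 it gives 1.3/1.1 of 21.5 against 2.6/2.5 of 26.4.

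**6. Proteomics-like model (7,000 proteins, 20 true).** FALSE: equal SDs 9.4 of 26.0; 10-fold 2.9 of 17.0; 100-fold 1.6 of 14.0. Standardized: 11.0 of 40.6.

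**7. Do the univariate results fill the gap?** They do not depend on scale. In the CyTOF layout (504 t-tests, equal SDs within block), of 5 true signaling features Bonferroni shows 1.4 and Benjamini-Hochberg 2.3. Of the 5 − 1.6 = 3.4 that the net misses at ratio 3, they show 0.6 and 1.2.

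**The case against.** - **Section 8.4 is not empty.** It specifies arcsinh transformation, visit differences and parent populations, and these may be the modifications 8.1 had in mind for CyTOF. But they define features without putting different types on one scale, and they do nothing for ActiGraph or RFU values.
- **Scaling may happen before the fitting call.** Switching off internal standardization is compatible with that. This stands: if features are pre-scaled, the problem does not arise. The SAP does not say so, however, nor whether any scaling is estimated inside the training folds.
- **The primary method itself was not simulated.** The SAP gives neither the iEN prior weights nor the number of stimulations, so the CyTOF figures describe a plain elastic net on Dataset 1 only. This stands, and they should not be read as expected losses for the primary endpoint.
- **Variance can carry information.** Most CyTOF features (462 of 504) share an arcsinh scale, and leaving them unscaled avoids inflating noisy, low-variance channels. A test built to favour this view used 462 features, 10 true, 40 trials, fixed measurement noise (SD 0.1) and effects proportional to biological SD. FALSE found 4.5 of 23.6 against 5.8 of 25.2 standardized. Under constant d = 1.2 the same layout gave 4.4 of 26.2 against 7.9 of 29.8. The loss shrinks from about 3.5 features to 1.3 but does not reverse, so its size depends heavily on assumptions.
- **The alpha = 0.5 point is secondary.** In most unequal-SD settings FALSE gives shorter lists, and the list of 112.5 needs all SDs at 0.05. The point is mathematically right but minor.
- **Consequences are bounded.** The combined model is optional, the study is an exploratory pilot, univariate results are planned, and 8.1 allows modifications to be noted in the study report.

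**Conclusion.** The concern holds. Section 8.1 departs from the default for every model, cites a justification that 8.4 does not contain, and as written makes feature selection depend on measurement scale. The dependence itself is exact (a factor of 60 for hours against minutes). Its practical size is conditional on SDs that the documents do not give: negligible if SDs are equal and near 1, about 1.3 of 5 true ActiGraph-like features lost at a tenfold spread (4.6 − 3.3), and complete loss of the CyTOF block from the combined model once protein SDs are three times larger.

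It is clearest for the mixed-unit ActiGraph model and the optional combined model. It also applies to CyTOF, where percentage points and arcsinh units are mixed, and to proteomics, where dynamic range in RFU differs between proteins. It should be fixed, but it does not threaten an efficacy conclusion.

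**What to change.** In SAP 8.1 and 8.4, state that every feature is z-scored with the mean and SD of the training fold before fitting.

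- **CyTOF (iEN):** z-score before any prior weights are applied, and leave the internal setting at FALSE.
- **ActiGraph, proteomics and any combined model:** set standardization to TRUE, or use the same z-scoring.
- **If scaling before the fit was already intended:** say so in 8.4.

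The cost is one or two sentences and a few lines of code, with no new data. One small downside is that low-variance, noise-dominated features are no longer held back by their scale; a detection or cell-count filter can handle that. If all SDs are already similar and near 1, results hardly change (7.7 true of 25.1 against 7.9 of 26.4 in the CyTOF illustration, both blocks together).

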10.4.2 ANALYSIS OF THE PRIMARY ENDPOINT

The study is not powered to detect significant changes in the immune signatures; however, using available data from analysis of this endpoint, including changes from baseline, the primary interest is to detect

immune features (and proteomic features) that separate the two groups. Machine learning approaches using cross-validation algorithms will be the primary approach for such analysis. The output of this analysis will produce a list of significant immune and/or proteomic features.

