11 APPENDICES

11.1 Appendix 1: Figure Descriptions/Shells

Figure 14.1.1: Subject Disposition (CONSORT Diagram)

[figure not shown]
[figure not shown]

Figure 14.2.1: Boxplot Comparing the Elastic Net Values from a Cross-validated Model of CyTOF Features Between the Active GRF6021 Group and Placebo Group

Note: The above figure is for illustration purposes only. The figure does not represent the data of the study. Colors and symbols may change. Axis titles or values may also change.

In figure 14.2.1, y-axis is the calculated Elastic Net Values from cross-validated model of CyTOF features.

[figure not shown]
Similar figures:

Figure 14.2.2: Boxplot Comparing the Elastic Net Values from a Cross-validated Model of ActiGraph Features between the Active GRF6021 Group and the Placebo Group

Figure 14.2.3: Boxplot Comparing the Elastic Net Values from a Cross-validated Model of Proteomics Features (SomaScan platform) Between the Active GRF6021 Group and the Placebo Group

Figure 14.2.4: Boxplot Comparing the Elastic Net Values from a Cross-validated Model of Combined CyTOF Features and Proteomics Features (SomaScan platform) Between the Active GRF6021 Group and the Placebo Group

Figure 14.2.5: Correlation Network of CyTOF Features Represented by a Minimum Spanning Tree

Note: The above figure is for illustration purposes only. The figure does not represent the data of the study. Colors and symbols may change. Axis titles or values may also change.

In Figure 14.2.5, each dot represented significantly associated features (after Bonferroni adjustment), different color indicated different feature types, such as cell frequency features and cell signaling features. Lines pointed the increased immune features in the GRF6021 group or in the placebo group.

[figure not shown]
Similar figures:

Figure 14.2.6: Correlation Network of ActiGraph Features Represented by a Minimum Spanning Tree

Figure 14.2.7: Correlation Network of Proteomics Features Represented by a Minimum Spanning Tree

Figure 14.2.8: Correlation Network of CyTOF and Proteomics Features Represented by a Minimum Spanning Tree from Combined CyTOF and Proteomics Data

Figure 14.2.9: Identified CyTOF Features Showing on the Correlation Network Based on Elastic Net Regression Models

Note: The above figure is for illustration purposes only. The figure does not represent the data of the study. Colors and symbols may change. Axis titles or values may also change.

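### SAP 8.1 names no metric, tuning loss or null reference for the cross-validated separation of the arms, and an ordinary t or rank test would not hold its level on nested leave-one-out scores

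*SAP*

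**What the plan says.** Protocol 10.4.2, on the primary endpoint: "Machine learning approaches using cross-validation algorithms will be the primary approach for such analysis". SAP 7.2 adds a hypothesis that the arms differ: "The hypothesis is that active treatment with GRF6021 will modulate the immune response and/or proteomics profiles to surgery differently as compared to placebo".

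SAP 8.1 sets out nested leave-one-out: "A two-layer leave-one-out cross-validation strategy will be employed where the final model will have optimized the segregation of active versus placebo treatment groups". It gives the role of each layer: "The internal layer will optimize the free parameters of the model, and the external layer will evaluate model performance". On the fitting it says "All parameters will be set to default except for" a mixing alpha of 0.5 and no standardization. It names R, but no package, model family, inner loss or rule for choosing the penalty, so the text does not settle what the defaults are. It then says: "Unless otherwise specified, an alpha of 0.05 will be used for significance testing". No sidedness is given, and no test is tied to the separation of the arms. Control across features is by Benjamini-Hochberg (BH).

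SAP 8.4.1 and 8.4.2 refer back to 8.1. Appendix 1 supplies the display, Figure 14.2.1: "Boxplot Comparing the Elastic Net Values from a Cross-validated Model of CyTOF Features Between the Active GRF6021 Group and Placebo Group". Figures 14.2.2 to 14.2.4 repeat it for ActiGraph, proteomics and the combined data. The description of Figure 14.2.5 marks features as significant after a Bonferroni correction.

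Protocol 10.4.1 lists a paired t-test, ANCOVA, rank-ANCOVA or other non-parametric methods for consideration on primary and secondary endpoints alike.

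**The concern.** The primary approach ends in two sets of cross-validated scores, one per arm. The plan does not say which number summarizes their separation, or what that number looks like when treatment does nothing. An analyst with two boxplots and a default alpha of 0.05 would naturally reach for a t or rank test, and that reference fails for two reasons.

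- **Composition.** Leaving out a subject shifts the arm share of the training set against that subject's own arm, which pushes held-out scores the wrong way.
- **Dependence.** Held-out scores share almost all their training data, so their AUC varies more than a test for independent observations assumes.

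At stake is whether the primary result can be told from chance. Favourable separation could be declared too often, and a strongly reversed result could be taken for a finding when it is an artefact.

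**Working it through.** There is no stated AUC, power or error rate to reproduce.

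**Inputs from the documents.** SAP 7.3: "enrollment ended with 37 evaluable subjects" (split by arm not given). Mixing alpha 0.5, unstandardized, inner and outer leave-one-out (SAP 8.1). Features: 62 for ActiGraph (SAP 8.4.2.1), about 7,000 proteins (SAP 8.4.2.2), and for CyTOF Dataset 1, from SAP Table 2, (21 frequencies + 21 × 11 signals) × 2 visits = 504.

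**Assumptions.** Split 18/19 or 14/23; Gaussian features in correlated blocks; standard elastic net; the losses and penalty rules shown below.

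**1. Closed form.** With n subjects, n1 on active and y = 1 for active, an intercept-only squared-error fit gives the held-out score (n1 − y)/(n − 1). At n = 37 that is (n1 − 1)/36 for each active subject and n1/36 for each placebo subject, a reversed gap of 1/36 = 0.028 at any split. At 18/19 the scores are 17/36 = 0.472 and 18/36 = 0.500. Every active subject ranks below every placebo subject, so the AUC is exactly 0 with no effect.

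**2. What an ordinary rank test assumes.** The SD of the AUC is √[(n + 1)/(12·n1·n2)] = √[38/(12 × 18 × 19)] = 0.096. The one-sided 5% cut-off is 0.5 + 1.645 × 0.096 = 0.66, and the two-sided 5% cut-off is 0.69.

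**3. Null simulations, pooled over six settings** (62, 504 or 7,000 features; blocks of 12, correlation 0.5; 1,017 runs; two-sided 5% rank test, nominal favourable rate 2.5%):

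| Penalty rule | Mean AUC by setting | Rejected | Favourable |
|---|---|---|---|
| lambda.min, squared error | 0.22 to 0.35 | 697 (68.5%) | 109 (10.7%; 6% to 13% by setting) |
| lambda.1se | 0.11 to 0.23 | 857 (84.3%) | 71 (7.0%; 1% to 9%) |
| three fixed penalties | 0.43 to 0.51 | 309 to 323 (30% to 32%) | 124 to 137 (12% to 13.5%) |

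At lambda.min, 697 − 109 = 588 rejections were reversed, and the null 95th percentile of AUC was 0.69 to 0.80 by setting. With fixed penalties the bias was small, but the SD of AUC was about 1.8 times the rank-test SD.

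**4. Second set of null runs, varying the inner criterion** (n = 37, 18/19, correlation 0.6; rank test, t test in brackets):

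| Features, criterion | Mean AUC | Rejected | Favourable |
|---|---|---|---|
| 504, squared error | 0.271 | 67% (64%) | 9.7% (8.1%) |
| 504, one-SE | 0.166 | 80% (75%) | 6.0% (5.0%) |
| 504, inner AUC | 0.471 | 29% (27%) | 10.6% (10.6%) |
| 62, inner AUC | 0.494 | 23% (19%) | 9.9% (10.7%) |
| 62, logistic deviance | 0.197 | 75% (71%) | 5.2% (4.3%) |

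The 504-feature rows rest on 517 runs, the 62-feature rows on 494 (inner AUC) and 791 (logistic). Over every nested setting run, total rejection was about 19% to 90%. An untuned nearest-centroid rule (3,000 null datasets, 504 features) also lost its level, with 18% rejected in total and 4.5% favourable.

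**5. Fitted instead of held-out values.** With 504 features, fitted scores of the final model gave a mean null AUC of 0.76 and 58% rejection, all favourable.

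**6. Permutation of the whole procedure.** Unrestricted, 62 features, 19 permutations, 287 null datasets: level 4.5%, although the mean AUC was 0.20. Within four strata, 504 features, 19 permutations: 7 of 124 (5.6%, 95% CI 2.3% to 11.3%). Both are one-sided at 5%. On the same 124 datasets the two-sided rank test rejected 13 in the favourable direction (10.5%), where its nominal rate is only 2.5%; the two counts are therefore not at the same nominal level.

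**7. Minor point.** With 504 features Bonferroni requires p < 0.05/504 = 9.9 × 10⁻⁵, which needs a 1.75 SD shift for 80% power at 18/19. BH needs about 1.47 SD if 10 features are declared and 1.27 SD if 50 are.

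**The case against.** The best defence is that the plan never promises a test of separation. Protocol 10.2 says the study is not designed to show significant differences on the primary endpoint, protocol 10.4.2 gives a list of features as the output, and SAP 8.1 controls false discovery across features. AUC appears in neither document. This stands as a limit on severity. It does not supply a chance reference for the model performance that the outer layer is meant to evaluate, and SAP 7.2 does hypothesize a difference.

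Several stronger readings are tempting but not supported:

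- **That the SAP prescribes an invalid test.** It prescribes none for these scores; protocol 10.4.1 only lists tests to consider.
- **That the null AUC is always far from 0.5.** The shift depends on the unnamed criterion. It is large under squared-error, deviance or one-SE tuning and small (0.47 to 0.51) under inner-AUC tuning, which the SAP's phrase about optimizing segregation could mean. The test level fails either way.
- **That the boxplots certainly show held-out scores.** The text speaks of values from a cross-validated model and also of a final model. Fitted values would be biased upward, not downward.
- **That the primary analysis has a 10.7% false-positive rate.** CyTOF is assigned to the immunological elastic net (iEN), whose weights are not given and which was not simulated. Rates also vary with implementation: a separate glmnet run gave 43% total rejection, against 60% to 75% by setting at lambda.min above.
- **That Appendix 1 shows no metric at all.** A value printed inside a missing figure cannot be excluded, though the shells are marked as illustrative only.

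**Conclusion.** The point holds as an omission with a practical consequence. The available text gives no metric, loss, penalty rule or null reference for the separation of the arms, and leaves open which scores are plotted. If the gap is filled with an ordinary two-sided 5% test on held-out scores, total rejection under the null is several times nominal and mostly reversed. Favourable rejection is usually about 4% to 14% against 2.5%, and below nominal in one lambda.1se setting.

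The closed-form result needs no simulation. The rates are illustrative and rest on an assumed split, correlation, loss and penalty rule, and on standard elastic net in place of iEN. The combined CyTOF and proteomics model was not simulated. Because the study is declared exploratory, this should be fixed but does not undermine the design. The BH and Bonferroni statements are a separate, minor contradiction; it affects the features marked in the correlation networks, not the elastic-net list in Figure 14.2.9.

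**What to change.** In SAP 8.1:

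1. State that Figures 14.2.1 to 14.2.4 plot outer-layer held-out scores.
2. Name the AUC of those scores as the metric, and state the inner loss and the lambda rule.
3. Take a one-sided p-value, (1 + number of permuted AUC ≥ observed)/(1 + B), for example with B = 1,000. Each permutation re-runs the whole nested procedure with arm labels permuted within the sex-by-joint strata of SAP 7.4. Validity rests on labels being exchangeable within strata.
4. Report the observed AUC beside the mean and 95th percentile of that null.
5. Apply no t or rank test to the scores; the boxplots carry only the permutation p-value.

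Separately, use the BH q-value in SAP 8.1 and in the Figure 14.2.5 description, and note that this supersedes protocol 10.4.8 (no multiplicity adjustment) for these analyses.

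**Cost.** No new data. In compiled code on one core a nested run took 0.5 to 1.2 s at 62 to 504 features and 2.6 to 7.8 s at 7,000. For 1,000 permutations that is about 8 to 20 minutes and about 43 minutes to 2.2 hours. R, iEN (not timed), the combined model and several visit changes per protein will take longer. The cut-off is stricter than that of the invalid rank test. With a 1 SD shift in 12 of 504 features, permutation detected 44 of 53 (83%) against 51 of 53 (96%); with a weaker signal (mean AUC 0.63) it was 32% against 52%.
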